IRB	Institutional Review Board
PBMC	peripheral blood mononuclear cell
RE	Radioembolization
UMN	University of Minnesota
Y90	Yttrium 90
XRT	External beam radiation

Protocol Synopsis

Radioembolization of Primary and Secondary Liver Malignancies and the Effect On the Immune System

CPRC #2018LS026

Study Design: This is a single institution non-interventional study designed to evaluate the immune reaction to radioembolization (RE) of primary and secondary malignancies of the liver.

RE has been established as a standard of care treatment for both primary and secondary cancers of the liver. The treatment consists of a mapping, or planning angiogram, followed by a delivery angiogram where the dose of yttrium 90 (y90) is delivered. Data has been published on the immune modification powers of external beam radiation (XRT). However, very little data is available on the ways in which RE modifies the immune system. The goal of this study is to determine changes in the peripheral blood monocytes, cytokines and the treated and untreated liver tumors through sample collection prior to and for 12 weeks after standard of care RE.

Prior to the RE delivery procedure, patients will have a blood draw to evaluate for levels of 11 immunologically relevant cytokines (IL-1 α , IL-1 β , IL-2, IL-6, IL-10, IL-12p70, IL-18, TNF α , IFN- γ , Fit ligand 3, and MCP-1). These blood draws will be repeated at 7 days (\pm 6 days), 4 weeks (\pm 2 weeks) and 12 weeks (\pm 2 weeks) after RE.

The patients will also have the infiltration of immune relative cells into treated tumors evaluated. This will be done by the patients undergoing biopsy of the largest tumor to be treated prior to treatment and optionally at 2 weeks (\pm 7 days) following RE. If patients have other areas of tumor, which are not included in the initial treatment site, these areas will also be biopsied.

Finally, the change in immunologically important peripheral lymphocytes will be collected. This will be done with a blood draw on the day of, but prior to RE serving as an internal control. Patients will then also have blood draws performed at 7 days (\pm 6 days), 4 weeks (\pm 2 weeks) and 12 weeks (\pm 2 weeks) after RE.

Primary Objective: Determine changes in the peripheral blood lymphocytes after radioembolization (RE) therapy for primary and secondary malignancies of the liver at 12 weeks.

Secondary Objectives:

- Determine changes in the peripheral blood cytokines after radioembolization (RE) therapy for primary and secondary malignancies of the liver.
- Determine the changes in infiltrating immune cells within the treated tumor, which occur after RE therapy for primary and secondary malignancies of the liver.

- Determine the changes in infiltrating immune cells within non-treated liver tumors, which occur after RE therapy for primary and secondary malignancies of the liver.
- Determine changes in the peripheral blood lymphocytes after RE therapy for primary and secondary malignancies of the liver at 7 days, 4 weeks, and 12 weeks.

Key Inclusion Criteria:

- Biopsy or image (in the setting of hepatocellular carcinoma (HCC)) diagnosed hepatic malignancy
- Total bilirubin < 2 mg/dL
- ECOG status ≤ 2
- Life expectancy >3 months assessed
- Age >22 years
- Lesion >2.0 cm which is amenable to percutaneously biopsied

Key Exclusion Criteria:

- Unwilling or unable to attend all study related follow ups
- Technetium 99 macro aggregated albumin (MAA) lung shunt fraction >20%
- Arterial anatomy which precludes the ability to safely perform RE
- INR > 3 or platelet count <15,000 which cannot be corrected
- Patients who are unable to hold anticoagulation and/or antiplatelet therapy in the peri-procedural setting

Accrual Objective:

The goal is to accrue 30 patients. It is anticipated that approximately 10 patients per year can be enrolled; meaning enrollment is expected to take 60 months.

1 Objectives

1.1 Primary Objective

The primary objective is to determine changes in the peripheral blood lymphocytes after RE therapy for primary and secondary malignancies of the liver.

1.2 Secondary Objectives

- Determine changes in the peripheral blood cytokine after REtherapy for primary and secondary malignancies of the liver.
- Determine the changes in infiltrating immune cell within the treated tumor which occur after RE therapy for primary and secondary malignancies of the liver.
- Determine the changes in infiltrating immune cell within non-treated liver tumors which occur after RE therapy for primary and secondary malignancies of the liver.

2 Background and Rationale

The importance of the immune system in the treatment of cancer has been well established over the last several decades, leading to the development of immunotherapies (1). It has also been noted that certain loco-regional therapies such as external beam radiation (XRT) and thermal ablation induce immunologic responses (2-6). However, to date basic research into the immune response induced by RE, a recently established standard of care treatment for primary and secondary malignancies of the liver, is lacking (7,8).

Rarely, loco-regional therapy can induce a positive immune response systemically, termed an abscopal effect. Pre-clinical studies with XRT have suggested that single high dose radiation, not clinically obtainable with XRT, but regularly performed in RE, make abscopal events more frequent (9-11). This suggest RE may be an excellent method of inducing abscopal effects as the deliverable dose to the tumor can be as high as 200-300 Gy, much higher than clinically obtainable by XRT (11). However, despite the apparent potential of RE to positively modulate the immune system and the dramatic benefits this may provide, little research has been performed in this area.

Five prior papers have investigated cytokine changes following RE (12-16). Both Carpizo et al and Lewandowski et al focused on the release of angiogenic factors which have been shown to be tumor protecting, however, are not focused on immunomodulation.

Wickremeskera et al did study changes in several immunomodulating cytokines (IL-1 β , IL-6, IL-8, IL-10, IL12, TNF α , and IFN-Y) however, only did so over the first 48 hours. The half-life of yttrium 90 is 64.1 hours, therefore much of the radiation dose and potentially the immunomodulation, will not have occurred at 48 hours. Fernandez-Ros et al. focused on the induction of liver regeneration following RE and through that studied among other factors the change in IL-6, IL-8, and TNF- α before and at 4 time points following treatment out to 2 months (15). Finally, Seidensticker et al. investigated the prognostic effects of IL-1, IL-2, IL-4, IL-6, IL-8, and TNF- α on overall survival and liver dysfunction with serum blood draws prior to and at 3 days and 6 weeks after radioembolization (16). They found that pre-

treatment IL-6 and IL-8 values portended a worse prognosis (16). These studies have also found that RE leads to modifications in several cytokines (IL-1 and IL-6) (12, 15, 16) however, they do not focus on the immunomodulatory capabilities of these cytokines, include a comprehensive cytokine profile, nor correlate cytokine changes with immune cell infiltration or peripheral lymphocyte changes.

Similarly, while the ability of XRT to induce immune cell infiltration has been investigated (17,18), this has not been documented in RE. Multiple cells including cytotoxic T cells, natural killer cells, helper T cells, dendritic cells, and macrophages have been shown to play roles in immune mediated tumor cell death and tumoral cell protection pathways (17). The infiltration of these cells into a treated tumor following RE is significant in the understanding of how RE induces immune modulation. Recently Chew et al published the first study to investigate immune cell infiltration following RE (19). The demonstrated higher expression of granzyme B and infiltration of CD8⁺ T cells, CD56⁺ NK cells and CD8⁺ CD56⁺ NK cells into treated tumors. They also demonstrate an increase in the TNF- α on both CD8⁺ and CD4⁺ T cells as well as an increase in the percentage of antigen presenting cells after RE.

3 Patient Selection

Study entry is open to patients 22 years of age and older regardless of gender, race, or ethnic background. While there will be every effort to seek out and include minority patients, the patient population is expected to be no different than that of other studies enrolling a similar population at UMN.

Non-English speakers will not be actively sought out for the purposes of this study, however, they would not be excluded given the availability of in house interpretive services.

Translation services will be provided for all participants who self-identify either as requiring translators or if it is felt by the investigator at any time to be necessary to utilize a translator to ensure full understanding of a concept or term. If a potential participant is non-English speaking, a written short form consent will be provided and reviewed with an interpreter. In addition, an interpreter will go through the main consent with the participant orally. If interested in the study, the participant will sign the short form, but not the full English consent form. A witness, who is not study staff or family, will sign both the short form and the main consent form. The study staff who is responsible for obtaining consent will sign only the main consent form. If the participant is expected to be participating for more than 30 days following the consenting process, the main consent will be translated into their language and provided to the participant. Once a long form consent is translated for a given language, only the long form and not the short form will be used with subsequent participants who speak that language. A potential participant must meet all of the inclusion and exclusion criteria to be considered eligible for study participation.

3.1 Inclusion Criteria

- 3.1.1 Diagnosis of primary hepatocellular carcinoma or biopsy proven hepatic metastases from another solid tumor primary for which RE is planned
- 3.1.2 Hepatic lesion >2.0 cm which is amenable to percutaneously biopsy

- 3.1.3 Age 22 years or older
- 3.1.4 EOCG PS ≤ 2 – refer to Appendix II
- 3.1.5 Total bilirubin ≤ 2.0 mg/dL
- 3.1.6 Expected life expectancy of >3 months assessed
- 3.1.7 Participant provides voluntary written consent prior to the performance of any research related tests or procedures

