3.2 Exclusion Criteria

- 3.2.1 Pregnant or breastfeeding - Females of childbearing potential must have a negative pregnancy test (serum or urine) within 7 days of study registration
- 3.2.2 Technetium 99 macro aggregated albumin (MAA) lung shunt fraction >20%
- 3.2.3 Arterial anatomy which precludes the ability to safely perform RE
- 3.2.4 INR > 3 or platelet count <15,000/mcL
- 3.2.5 Patients who are unable to hold anticoagulation and/or antiplatelet therapy in the periprocedural setting
- 3.2.6 In the opinion of the enrolling investigator, the patient may be unwilling or unable to attend all study related follow up due to physical, psychiatric, or logistical circumstances

3.3 Anticipated enrollment time line:

It is anticipated that approximately 10 patients per year can be enrolled in this study. Therefore, it is believed that it will take approximately 60 months to enroll the goal of 30 patients.

4 Patient Registration and Study Enrollment

Written consent must be obtained prior to the performance of any research related tests or procedures. Consent is usually obtained before final eligibility is determined.

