4.2 Study Enrollment with the Masonic Cancer Center Clinical Trials Office

To be eligible for study enrollment, the patient must sign the research consent and meet each of the inclusion criteria and none of the exclusion on the eligibility checklist (Appendix I) based on the eligibility assessment documented in the patient's medical record.

The Primary Clinical Research Coordinator (PCRC) or designee will add the "on-treatment" date to complete enrollment.

5 Study Plan

Patients enrolled in this study receive standard of care (RE therapy but agree to serial sample collections for research purposes as detailed in Section 7.

Direct study participation ends after the final blood sample is collected 12 weeks after the RE therapy unless any of the following occurs:

- The patient is non-compliant or withdraws consent
- The patient is discharged to hospice for terminal cancer care

As part of the consent process, the participant will be asked to opt in to the storage of any leftover blood or tumor samples for future unspecified research once testing related to this study is completed and verified.

6 Expected Adverse Events and Potential Risks

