Patients will undergo biopsy of the largest percutaneous available tumor to be treated within a 12-week period prior to treatment and optionally at 2 weeks (\pm 7 days) following RE. If the pre-treatment biopsy is not standard of care, it will be done for research. The 2-week after treatment biopsy will be performed strictly for research purposes. The optional post RE biopsy will include a treated (defined as a lesion which had y90 delivered to it as determined on standard of care Bremsstrahlung scan after RE) and non-treated lesion (defined as a lesion which did not receive y90 as determined on standard of care Bremsstrahlung scan after RE). Four 18-gauge core needle biopsies will then be obtained. One of the four cores will immediately be placed on ice and sent to our CLIA approved research laboratory. This sample will then be flash frozen and

stored at -80 degrees. Three of the cores will immediately be placed into formalin and submitted to the research laboratory where they will undergo paraffin embedding. These samples will also be stored until analysis can be undertaken. A paraffin embedded sample will then undergo immunohistochemistry analysis. The samples will be analyzed using a standard streptavidin biotinylated alkaline phosphatase method or a streptavidin biotinylated horseradish peroxidase method as described previously (17,18). The slides will then be analyzed using a standard light microscope and CCD-camera at 20x objective. The slides will be scanned into digital format using an Aperio XT scanner (Leica Biosystems Inc. Buffalo Grove, IL). A pathologist will then demarcate the tumor area on the slide. This area of interest will be analyzed using the counting software "FiJI-ImageJ" (FIJI) will be used to quantify the number of infiltrating cells (cell/mm²) in the tumor. They will also be analyzed by the number of infiltrating cells per 100 tumor cells. These analytic standards have been previously described (17,18). The infiltration of immune cells into the tumor before and after treatment will then be compared with each patient serving as their own control.

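### The scan-only definition of a non-treated lesion admits lesions treated earlier with RE, external beam radiation or ablation, and eligibility does not keep them out

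*Combined protocol and SAP*

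**What the plan says.** **Eligibility.** Criterion 3.1.1 reads "Diagnosis of primary hepatocellular carcinoma or biopsy proven hepatic metastases from another solid tumor primary for which RE is planned". RE has to be planned; it does not have to be the first. The exclusions in 3.2 that bear on RE concern whether it can be given safely: a lung shunt fraction above 20%, and "Arterial anatomy which precludes the ability to safely perform RE". Neither 3.2.1 to 3.2.6 nor the key criteria in the Synopsis set an exclusion or a washout for earlier RE, XRT or ablation.

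**Lesion rule.** Section 7.4 describes the second lesion sampled at the optional post-RE biopsy as a "non-treated lesion (defined as a lesion which did not receive y90 as determined on standard of care Bremsstrahlung scan after RE". The definition has no condition on earlier treatment.

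**Biopsy schedule.** The 7.2 table names an untreated tumor only in the optional 2-week column. Section 7.3 likewise places that biopsy two weeks after treatment, when such a lesion is available. The pre-treatment biopsy in 7.4 is of the largest accessible tumor that is to be treated.

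**Blood baseline.** The Synopsis specifies a "blood draw on the day of, but prior to RE serving as an internal control". There is no comparison group.

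**Data and analysis.** Section 7.4 records type of malignancy, size of the largest tumor and number of tumors. Section 7.1 takes a general medical history. Section 10 names age, sex and tumor size as possible covariates; prior liver-directed therapy is not named.

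**The concern.** Changes in immune cells within non-treated liver tumors are a named secondary objective, and the abscopal effect is the hypothesis that Section 2 sets out. That objective needs lesions that have not themselves received a treatment capable of drawing in immune cells. Section 2 states that "certain loco-regional therapies such as external beam radiation (XRT) and thermal ablation induce immunologic responses", so by the protocol's own account an earlier local treatment is a competing explanation for an infiltrate. If the rule lets such a lesion count as non-treated, a local effect of old treatment can be reported as a systemic effect of the study RE.

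The blood endpoints raise a related but weaker question. A patient who arrives for a repeat RE has a baseline drawn after an earlier RE, and no planned data item or analysis would show this.

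**Working it through.** The documents give no power or sample-size calculation, so there is no planned figure to reproduce. The check has three parts.

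**1. Can the scan reveal an earlier RE?**

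Input: yttrium-90 half-life 64.1 hours (Section 2). By physical decay, the fraction of activity remaining after *d* days is 2^(−24*d*/64.1).

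| Days since earlier RE | Half-lives elapsed (24*d*/64.1) | Activity remaining |
|---|---|---|
| 7 | 2.62 | 16.3% |
| 14 | 5.24 | 2.6% |
| 21 | 7.86 | 0.43% |
| 28 | 10.48 | 0.07% |

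Time to fall below 1%: log2(100) × 64.1 / 24 = 6.64 × 64.1 / 24 = 17.7 days. Time to fall below 0.1%: log2(1000) × 64.1 / 24 = 9.97 × 64.1 / 24 = 26.6 days.

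The documents give no detection limit for the scan. I assume that activity below 0.1% would not be seen. Within the first two to three weeks some activity might still be visible, so the failure is clear only from about a month onward.

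**2. Can the scan reveal earlier XRT or ablation?**

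No, at any interval. Neither delivers yttrium-90, so a scan for yttrium-90 carries no information about them.

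**3. Would anything else in the plan catch the lesion?**

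- Eligibility: 3.1 and 3.2 contain no relevant criterion.
- Recorded data: the tumor characteristics in 7.4 do not include prior therapy. The history in 7.1 may contain it, but no rule uses it to classify lesions.
- A pre-RE sample of the same lesion: 7.2 and 7.3 name the untreated lesion only after RE, and 7.4 directs the pre-treatment biopsy to a tumor that will be treated. Section 10 plans paired tests for non-treated tumors, but the schedule does not clearly supply the first member of the pair. Without it, an infiltrate that was already present cannot be told from a new one.

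Misclassification therefore requires three things together: the lesion was treated earlier (by RE about a month or more before, or by XRT or ablation at any time), it is not targeted by the study RE, and it is chosen for the optional biopsy. The documents permit each of these and give the frequency of none.

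**The case against.** **The Synopsis points to a first treatment.** It refers to tumor outside the initial treatment site, which suggests enrolment around a first session with other lesions still untouched. This is fair as a hint of intent. It is not an eligibility criterion, it also implies that further sites may be treated, and it says nothing of XRT or ablation.

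**The definition is ambiguous rather than wrong.** It does not say which RE the scan follows. If the scan is standard of care, an earlier session should have had one too, and a lesion that took up yttrium-90 then could be read as failing the definition. That reading is available for earlier RE, but the text does not require anyone to retrieve an earlier scan, and it cannot help with XRT or ablation.

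**A paired sample would protect the comparison.** The Synopsis can be read as sampling other tumor areas before and after RE. An old, stable infiltrate would then sit in both samples and largely cancel. This is correct where a pair exists, but 7.2 and 7.3 do not schedule the pre-RE half.

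**The blood comparison survives.** A reader might infer that the baseline is invalid, or that the primary result is biased toward no change. The documents do not support that. The draw still directly precedes the study RE, so the paired change still describes what follows that RE. Dilution would need the first response to persist and to blunt the second, which nothing in the protocol establishes. Baseline adjustment in Section 10 allows for different starting levels, though it cannot tell a shifted baseline from a natural one.

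**Part is already within reach.** Medical history is taken and the covariate list is open-ended, so prior RE could be examined. That shows the fix is cheap; it does not prespecify anything. Only the heading of the Appendix I checklist is in the text available, so its content could not be checked.

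**Conclusion.** The point stands for the lesion definition. As written, it accepts a lesion irradiated by RE about a month or more earlier and not re-targeted, and any non-targeted lesion previously treated with XRT or ablation. Such a lesion, if biopsied, could be analysed as non-treated and its infiltrate misread as abscopal. The decay figures rest on the protocol's half-life and on the assumption that activity under 0.1% is not seen on the scan.

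How many lesions this would affect is unknown. It would be wrong to conclude that every earlier-treated lesion is misclassified: a re-targeted lesion is correctly called treated, and recent RE may still be visible. Because the post-RE biopsy is optional and an untreated lesion is sampled only when available, the affected number may be small, but so may the set it falls in.

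For the blood endpoints the conclusion is limited: a baseline may reflect earlier RE, and the plan would not identify it. The share of patients with prior RE is not stated. For scale only, an assumed 10% to 20% would be 30 × 0.10 = 3 to 30 × 0.20 = 6 patients; neither percentage has a source in the documents. A reader might infer that patients with prior RE must be excluded. The documents do not compel this, and with about 10 patients a year expected it is a trade-off against accrual.

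**What to change.** 1. In 7.4, define a non-treated lesion as one that did not receive yttrium-90 on the scan after the study RE and has not previously been treated with RE, ablation or external beam radiation, as established from the medical history taken under 7.1.
2. Add prior liver-directed therapy (type, date and lesion) to the malignancy characteristics recorded under 7.4.
3. In Section 10, prespecify a sensitivity analysis of the primary before/after change limited to patients without prior RE.

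An exclusion for prior RE in 3.2 is an option for the sponsor to weigh against accrual; items 1 to 3 do not depend on it.

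Cost: one revised definition, a few data fields drawn from history already collected, and one extra analysis. No new procedure is needed. A few lesions may no longer qualify as non-treated, which reduces an already optional sample.

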3.2 Exclusion Criteria

- 3.2.1 Pregnant or breastfeeding - Females of childbearing potential must have a negative pregnancy test (serum or urine) within 7 days of study registration
- 3.2.2 Technetium 99 macro aggregated albumin (MAA) lung shunt fraction >20%
- 3.2.3 Arterial anatomy which precludes the ability to safely perform RE
- 3.2.4 INR > 3 or platelet count <15,000/mcL
- 3.2.5 Patients who are unable to hold anticoagulation and/or antiplatelet therapy in the periprocedural setting
- 3.2.6 In the opinion of the enrolling investigator, the patient may be unwilling or unable to attend all study related follow up due to physical, psychiatric, or logistical circumstances

3.3 Anticipated enrollment time line:

It is anticipated that approximately 10 patients per year can be enrolled in this study. Therefore, it is believed that it will take approximately 60 months to enroll the goal of 30 patients.

4 Patient Registration and Study Enrollment

Written consent must be obtained prior to the performance of any research related tests or procedures. Consent is usually obtained before final eligibility is determined.

